2. Clinical Trial – With 40 participants randomized to each group, we will have 80% power to detect an effect size of $d=0.64$ for the treatment vs. control compassion. The effect sizes related to messaging interventions for depression have not yet been tested across enough trials to estimate effect sizes. However, meta-analyses comparing coached DMHIs to control conditions have shown effect sizes of $gs=0.67-0.70$ for depression and anxiety, which is not significantly different from psychotherapy.⁴¹ Effect sizes for self-guided DMHIs and smartphone interventions are considerably smaller ($gs=0.27-0.43$).^{42,43} It should be noted that choice of control condition can have a substantial impact on effect sizes. For coached DMHIs, the effect-size for trials using WLCs is $g=0.90$, while effect sizes for studies using active controls is understandably smaller, $g=0.38$.⁴¹ Thus, we would expect to see an effect size of approximately $d=0.38$ for treatment vs. control, as these analyses will pool participants across both engaged participants, who do not require a coach, and coached participants. While we acknowledge this effect size is lower than the effects we are powered to detect, it serves as a useful benchmark in determining whether the intervention shows sufficient value to pursue a larger trial.

As the use of machine learning to personalize messages is novel, there are no studies that provide ideal guidance as to the expected effect size for the adaptive vs. randomized intervention comparisons for DMHIs. However, there is considerable research using “computer-tailored” messaging for health behaviors (e.g. smoking cessation, physical activity, diet, mammography). A meta-analysis showed effect sizes of $g=0.12-0.22$ for tailored vs. randomized messaging.³⁵ These algorithms are simpler than those proposed here, typically consisting of decision trees that tailor only on baseline participant characteristics. Based on this literature, we would expect an effect size of approximately $d=0.20$ in analyses comparing the randomized and adaptive arms. Such an effect size would warrant the inclusion of the proposed machine learning algorithms to personalize messages to meet the needs and preferences of users.

- a. Active Control Group (n=40)
- b. Automated Intervention (n=40)
- c. Randomized Intervention (n=40)

4.0 Recruitment and Screening Methods:

(1) Longitudinal Usability Testing:

The sample will be recruited from two sources:

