13.0 Waivers and Alterations of Consent Information:

N/A

14.0 Financial Compensation:

DESIGN STUDY

Longitudinal Usability Testing

Wave 1 (8-week intervention):

Participants will be compensated \$20 for completing baseline measures and the initial set-up call, and \$20 for each subsequent assessment point (Week 4 & 8), and \$20 for each of the 2 interviews (Week 4 & 8). Amounting to a total potential earning of \$100 per participant. Compensation will be offered in the form of an electronic Amazon gift card or check.

Wave 2 (4-week intervention):

Participants will be compensated \$20 for completing the 4-week surveys, and \$20 for completing the 4-week interview. Amounting to a total potential earning of \$40 per participant. Compensation will be offered in the form of an electronic Amazon gift card or check.

CLINICAL TRIAL

We will reimburse all trial participants for completing research assessments. Participants will be compensated \$25 per major assessment session (Baseline, Week 4, 8, 12, 16; we note that a subjective engagement questionnaire will be administered to those in the intervention group at week 1, but due to brevity this is not considered a major assessment point). Amounting to a total potential earning of \$125 per participant. Compensation will be offered in the form of an electronic gift card or check.

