Statistical Analysis Plan for clinicaltrials.gov

Official Title: Digital Mental Health Service for Non-Treatment Seeking Young Adults

NCT Number: NCT04948268

Grant Number: R34MH124960

Northwestern University Social and Behavioral Institutional Review Board Number: STU00214822

Statistical Analysis Plan

Aim 2. Feasibility

The primary aim of this study will be to evaluate the feasibility of conducting a larger SMART trial. Feasibility will be determined by:

1. meeting recruitment and enrollment goals;
2. obtaining at least 80% of follow up self-report data at primary endpoints; and
3. maintaining dropout below 30% across treatment conditions.

Descriptive statistics will be used to summarize recruitment, retention, completeness of self-report measures, and patterns of missing data. These analyses will inform the suitability of procedures for a future fully powered trial.

Aim 2a. Effectiveness of messaging interventions relative to active control

To evaluate the effects of the adaptive and randomized messaging interventions relative to the control condition, we will model trajectories of the primary outcome (psychological distress; K10) and secondary outcomes (PHQ-9, GAD-7, DSI-SS, and CB-RSS). For each outcome, we will estimate a generalized linear mixed model (GLMM) with one model per outcome, fixed effects for treatment arm, time, and the treatment by time interaction, a participant-level random intercept, an autoregressive correlation structure for repeated observations, and an identity link for normally distributed outcomes, with alternative link functions used as appropriate based on distributional properties. The primary inference will focus on the treatment by time interaction to determine whether either intervention produces a different rate of change over time compared to control. Secondary models will control for baseline demographic covariates (e.g., age, sex, race, ethnicity).

Controlling for missing data and bias. Should more than 5% of the outcome data be missing, we will examine the data for missing mechanisms and use multiple imputation rather than complete case analysis for the primary analysis to avoid bias, combining results from 5 imputed datasets using “mice”.

Aim 2b. Effectiveness of adaptive versus randomized messaging

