If the treatment by time interaction indicates a significant difference between at least one messaging intervention and the control group for a given outcome ($p < .05$), as described in 2a, we will compare the adaptive and randomized messaging interventions for that outcome using the same GLMM approach, restricted to the 2 treatment arms. Outcomes will include the primary clinical outcome measure (K10) and secondary outcome measures (PHQ-9, GAD-7, DSI-SS, CB-RSS). The second primary outcome, engagement duration (time from first message received to last participant interaction), will be summarized descriptively by reporting means and standard deviations, and will be further explored using distribution-appropriate comparisons, as needed.

Aim 2c. Effectiveness of coaching for early disengagement

Participants in the intervention arms who meet predefined criteria for disengagement during the first 2 weeks will be re-randomized to receive coaching or continue without coaching. Analyses will use the same GLMM methods described in Aim 2a incorporating coaching as a covariate to explore whether coaching improves: engagement outcomes (engagement duration, response percentage, number of URL clicks), outcomes (K10, PHQ-9, GAD-7, DSI-SS, CB-RSS). Given the limited statistical power for this embedded re-randomization, results will be summarized descriptively, reporting model coefficients and confidence intervals rather than conducting formal hypothesis tests.

Aim 2d. Exploratory predictors of early disengagement

The need for coaching will be defined as meeting the disengagement criterion during the first 2 weeks. We will compare baseline demographic, clinical, and attitudinal variables between participants who do and do not meet this criterion. Continuous variables will be compared using the Wilcoxon rank sum test, and categorical variables will be compared using Pearson's chi squared test or Fisher's exact test when expected cell counts

are small.

In addition, exploratory predictive models such as random forests will be considered to evaluate whether combinations of baseline variables can classify participants who are likely to disengage early. These analyses are exploratory and intended to generate hypotheses for future trials.

Aim 3. Experimental therapeutics modeling

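### SAP Aim 2a tests a difference in slope without a participant random slope or robust standard error, so the test is modestly anti-conservative if participants change at different rates

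*SAP*

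**What the plan says.** SAP Aim 2a fits one generalized linear mixed model per outcome (K10, PHQ-9, GAD-7, DSI-SS, CB-RSS) with "fixed effects for treatment arm, time, and the treatment by time interaction". The dependence among a participant's repeated measures is carried by "a participant-level random intercept, an autoregressive correlation structure for repeated observations". The target of the test is explicit: "The primary inference will focus on the treatment by time interaction to determine whether either intervention produces a different rate of change over time" compared with control.

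The SAP names no random slope, no sandwich standard error, and no rule for checking or replacing the covariance structure. It does not state the order of the autoregressive process, whether the residual variance is constant over visits, or whether time is linear or categorical. Linear time is implied by the reference to a rate of change.

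The model is reused. Under Aim 2b, the adaptive and randomized arms are compared on an outcome only if the interaction separates at least one messaging arm from control at p<.05. Aim 2c uses the same methods with coaching as a covariate and reports coefficients with confidence intervals. If more than 5% of outcome data are missing, results are pooled over 5 imputed datasets.

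**The concern.** A random intercept lets participants start at different levels but gives them all the same expected slope within an arm. Real variation in slopes then has to be absorbed by the residual structure. An autoregressive term absorbs part of it, because it makes nearby visits more alike than distant ones, but it does not reproduce the way slope variation accumulates over follow-up. The variance left out is the variance that matters for a slope contrast, so the contrast looks more precise than it is.

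The design makes common slopes unlikely. Within each messaging arm, participants who disengage early are re-randomized to coaching or no coaching (Protocol 8.1, Clinical Trial). The adaptive arm delivers different content to different people. Aim 2d presumes that participants differ in their need for support.

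What is at stake is the error rate of the test that opens Aim 2b and the width of the intervals that are the reported result of Aim 2c.

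**Working it through.** **The plan's own figure.** Protocol 3.0 gives 80% power for d=0.64 with 40 per group. A two-sided 5% t test with 40 against 40 gives 80.7%, and 80% is reached at d=0.634. The figure reproduces, but it is a simple two-group calculation and says nothing about the repeated-measures covariance.

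**Inputs from the documents.** There are 40 participants per arm (Protocol 3.0) and five equally spaced assessments, at baseline and weeks 4, 8, 12 and 16 (Protocol 14.0). Alpha is 0.05 (SAP Aim 2b), taken as two-sided because the SAP does not say.

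**Assumed inputs.** The documents give no K10 SD, correlation or slope SD. I take intercept SD 5 and residual SD 4 with independent residuals, so the baseline SD is √(25+16) = 6.4. The SD of individual 16-week change due to slopes, s, ranges from 0 to 7 points. Data are complete, time is linear, and the planned structure is read as first-order with constant variance.

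**Method.** Let t = (0, ¼, ½, ¾, 1), let J be the all-ones matrix, and let Z have columns 1 and t.

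1. True covariance: S = 25·J + s²·tt′ + 16·I.
2. Planned structure: V = τ²·J + ω²·ρ^|i−j|, with τ², ω² and ρ chosen to minimise log|V| + tr(V⁻¹S). This is where the fit settles in large samples.
3. Model-based slope variance per participant: the slope element of A = (Z′V⁻¹Z)⁻¹. Actual variance: the slope element of HSH′, with H = AZ′V⁻¹.
4. Standard error of a between-arm contrast: √(2 × variance / 40). With r = actual SE / model SE, the real type I error is 2(1 − Φ(1.96/r)).

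| s (points over 16 weeks) | model SE | actual SE | r | type I error |
|---|---|---|---|---|
| 0 | 1.131 | 1.131 | 1.000 | 5.0% |
| 1 | 1.144 | 1.153 | 1.008 | 5.2% |
| 2 | 1.182 | 1.217 | 1.029 | 5.7% |
| 3 | 1.245 | 1.317 | 1.058 | 6.4% |
| 5 | 1.442 | 1.600 | 1.109 | 7.7% |
| 7 | 1.728 | 1.955 | 1.132 | 8.3% |

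**Hand check at s = 3.** The slope variance per participant is close to 9 + 16/Σ(t−½)² = 9 + 16/0.625 = 34.6. Then √(2 × 34.6/40) = 1.315, which agrees with the actual SE of 1.317. And 1.96/1.058 = 1.853, whose two-sided tail is 6.4%.

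**Wider assumptions.** In baseline-SD units, I took intercept variance shares of 0.5-0.7, residual autocorrelation 0 or 0.3, and slope SD 0.3-1.0. The type I error per contrast is then 5.3-8.3% for the constant-variance form and 5.1-7.3% if variances may differ by visit. A random intercept with no autoregressive term would give 6.0-20.5%, so the autoregressive term does much of the work, but not all of it.

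**Simulation.** I used three arms of 40, REML, Wald tests, intercept share 0.6, independent residuals and 2,000 trials per scenario (Monte Carlo error about 0.5 percentage points at 5%).

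| slope SD (baseline SDs) | planned model, per contrast | with random slope, per contrast | planned, either contrast | random slope, either contrast |
|---|---|---|---|---|
| 0 | 4.7-5.5% | 4.3-5.1% | 9.1% | 8.4% |
| 0.5 | 6.2-6.6% | 4.8-5.1% | 11.6% | 9.1% |
| 1.0 | 7.8-8.5% | 4.6-4.7% | 14.4% | 8.4% |

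The either-contrast columns correspond to the Aim 2b gate. That they sit near 9% even with a correct model comes from testing two contrasts, which is a separate matter. Only the excess over that belongs to this point. With residual autocorrelation 0.3, the random-slope model gave 4.4-6.2% per contrast.

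**The case against.** The strongest reply is that the effect is small and rests on assumption. A random intercept with an autoregressive residual is a recognised model. If slopes vary by only 1-2 points, the error rate rises by 0.7 percentage points at most. The 7-point case needs the K10 SD to grow from 6.4 to √(41+49) = 9.5 by week 16, a 48% increase. The calculation uses complete data, while the plan aims for 80% completeness and would pool over imputations. Feasibility is the primary aim, Aim 2c is descriptive, and Protocol 3.0 concedes that the expected d=0.38 is below what the trial can detect. All of this stands, and it limits the weight of the point. It does not change the direction: every non-zero slope SD examined gave a slope standard error that was too small.

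The reply is also right that constant variance and first order are software defaults, not SAP text. The heterogeneous-variance result covers that gap: the inflation is smaller but remains.

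A reader might go further and infer that intervals will be wrong in both directions, by looking at change to week 8 or week 16. The documents do not support that as a criticism of the primary inference. The SAP names no visit-specific K10 contrast as primary, and the direction of error at week 8 depends on which covariance is assumed. A reader might also infer that this p-value alone opens the mediation analysis. Aim 3 requires significant effects on both outcome and target, is labelled exploratory, and applies a 10% false discovery rate.

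**Conclusion.** The concern holds in a limited form. The SAP bases its test on differences in slope and leaves out between-participant slope variation, with no robust standard error as protection. If slopes vary, a nominal 5% contrast runs at about 5.2-5.7% for a 16-week change SD of 1-2 points and 6.4-8.3% for 3-7 points, given intercept SD 5, residual SD 4, complete data, linear time and a constant-variance first-order structure. If slopes do not vary, there is no error. The size is therefore modest and conditional on variances that the documents do not give. The correction is worth making before the analysis because the test is used as a gate and the change is cheap. It does not threaten the feasibility objective.

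**What to change.** Amend SAP Aim 2a as follows.

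- **Approximately normal outcomes, including K10:** either add a participant random slope for time, or use an unstructured covariance over the five visits (5×6/2 = 15 parameters, 120 participants). If unstructured is chosen, drop the separate random intercept, which it makes redundant, and name the random intercept and slope model as the fallback for non-convergence.
- **Non-normal outcomes:** use participant-clustered robust standard errors with a small-sample correction.
- **Time:** state whether it is linear or categorical, so that the interaction test is defined. If an autoregressive term is kept, state its order and variance form.
- **Degrees of freedom:** specify a small-sample method that works with the planned pooling over imputed datasets. Kenward-Roger degrees of freedom apply within one completed dataset, so the SAP must say how they enter the pooled test.

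Aims 2b and 2c inherit the change. The cost is a short paragraph, a few more covariance parameters, a named fallback, and slightly wider intervals where slopes vary (about 6% wider at a change SD of 3 points: 1.317/1.245 = 1.058).

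### The protocol sets effect-size benchmarks of d = 0.38 and d = 0.20, but the SAP pre-specifies no estimate to read against either, and its p < .05 gate can leave the second one unestimated

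*SAP*

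**What the plan says.** Protocol section 3.0 (Sample Size, Clinical Trial) states "80% power to detect an effect size of $d=0.64$ for the treatment vs. control", with 40 participants per group. It then says "we would expect to see an effect size of approximately $d=0.38$ for treatment vs. control" and concedes that "we acknowledge this effect size is lower than the effects we are powered to detect". The smaller figure is kept because "it serves as a useful benchmark in determining whether the intervention shows sufficient value to pursue a larger trial". For adaptive versus randomised messaging the same section expects d of about 0.20 and adds: "Such an effect size would warrant the inclusion of the proposed machine learning algorithms to personalize messages to meet the needs and preferences of users".

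The SAP, Aim 2a, fits a mixed model with arm, time and their interaction. It states: "The primary inference will focus on the treatment by time interaction to determine whether either intervention produces a different rate of change over time compared" with control. Aim 2b is conditional: "If the treatment by time interaction indicates a significant difference between at least one messaging intervention and the control group for a given outcome" at p < .05, the two messaging arms are then compared on that outcome with the same model. For Aim 2c, citing limited power, the SAP commits to coefficients and confidence intervals in place of formal tests. It makes no such commitment for Aims 2a and 2b. Neither 0.38 nor 0.20 appears in the SAP.

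**The concern.** The two documents describe the K10 result on different scales. The protocol's yardsticks are standardised between-group differences, kept even though significance at 0.38 was not expected. The SAP's quantity is a difference in slope, in K10 points per unit of time, and it cannot be set against 0.38 without a visit and an SD.

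The gate makes this more than a missing detail. The comparison that the 0.20 yardstick refers to is not run on K10 unless an underpowered test first succeeds. A pilot that performs as the protocol expects could therefore end without any planned K10 estimate of what the algorithm adds.

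**Working it through.** **Inputs.** From protocol section 3.0: 40 per arm, three arms, detectable d = 0.64 at 80% power, expected d = 0.38 (messaging versus control) and 0.20 (adaptive versus randomised). From SAP Aims 2a and 2b: arm-by-time interaction, p < .05, at least one arm versus control. Assumed: two-sided tests, no multiplicity adjustment (the SAP states none for these aims), unit SD and complete data.

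**1. The plan's own figure.** SE of d = sqrt(1/40 + 1/40) = 0.2236. Noncentral-t power at d = 0.64 with 78 df is 80.7% (normal approximation 81.7%). The stated 80% is reproduced. It is a two-group comparison at one time point, not a calculation for the interaction.

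**2. The same comparison at the benchmarks.**
- Smallest observed d with p < .05: 1.991 × 0.2236 = 0.445.
- Observed d = 0.38: t = 0.38/0.2236 = 1.70, p = 0.093, 95% CI 0.38 ± 0.445 = −0.07 to 0.83.
- Power at true d = 0.38: 39%. At true d = 0.20: 14%.
- With 32 per arm (20% missing, the edge of the SAP's completeness target): threshold 0.50, power at 0.38 of 32%.

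**3. How often the Aim 2b gate opens.** Three arm means were simulated with variance 1/40, true values 0 (control), 0.38 and 0.38, and the control shared between the two tests. At least one test is significant in about 55% of 400,000 replicates. The gate stays shut in about 45% of trials on the at-least-one rule the SAP uses, and in 61% if only one arm is counted.

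**4. Sensitivity to the model the SAP actually uses.** Assume visits at weeks 0, 4, 8, 12 and 16, time entered linearly, and a between-arm difference of 0, 0.19 and 0.38 at weeks 0, 4 and 8. It then either stays at 0.38 (plateau) or falls to 0.285 and 0.19 (fade). Let s be the random-intercept share of variance.
- With independent residuals, slope SE = sqrt((2/40)(1 − s)/160), where 160 is the sum of squared time deviations.
- Plateau slope = (−4×0.19 + 4×0.38 + 8×0.38)/160 = 3.80/160 = 0.02375.
- At s = 0.3: SE 0.0148, z = 1.61, power 36%. At s = 0.7: SE 0.0097, z = 2.45, power 69%.
- Letting the lag-1 residual correlation run from 0 to 0.3 gives, for one arm, 32–48% (plateau, s = 0.3–0.5), 62–69% (plateau, s = 0.7) and 12–16% (fade, s = 0.3–0.5). If the effect instead keeps growing linearly to week 16, power exceeds 84% even at s = 0.3.

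**5. Why a week-8 value cannot simply be read off a straight line.** With five equally spaced visits and independent residuals, the fitted line at week 8 is the mean of the five differences. Plateau: (0 + 0.19 + 0.38 + 0.38 + 0.38)/5 = 0.266. Fade: (0 + 0.19 + 0.38 + 0.285 + 0.19)/5 = 0.209. With lag-1 correlation 0.3 the values are about 0.26 and 0.19. The true week-8 difference is 0.38 in every case.

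**6. Precision of a week-8 contrast.** For an unadjusted change from baseline with baseline-to-week-8 correlation r, SE = sqrt(2(1 − r) × 2/40). At r = 0.3 this is 0.265; at r = 0.545 (s = 0.5, lag-1 correlation 0.3) it is 0.213. Multiplying by 1.96 gives about ±0.52 and ±0.42 SD.

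**The case against.** The protocol attaches no decision rule, estimator or visit to 0.38, and the SAP makes feasibility (recruitment, follow-up completeness, dropout) the primary aim. A reader might infer that 0.38 decides whether a larger trial goes ahead; the documents do not support that. It is one consideration beside the feasibility criteria.

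A reader might also infer that a non-significant Aim 2a result would be reported as no difference, or that the benchmark will never be examined. Neither follows. The model yields coefficients, nothing in the SAP forbids deriving or reporting an effect size, and p < .05 is written as a gate to Aim 2b, not as a verdict on the programme.

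The range in which an observed d meets 0.38 yet misses significance is narrow: 0.38 to 0.445 on a single-visit comparison. It nearly vanishes if the arms are pooled (threshold 0.383 for 80 versus 40), although the SAP tests each arm. Adjusting for baseline can close it: with a baseline correlation of 0.5 the threshold is about 0.38. Nor can one say that a benchmark-level effect would usually miss significance, since the slope test's power runs from 12% to above 84% under shapes and correlations the documents leave open.

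These objections limit how strongly the consequence can be put. They leave two facts untouched: no estimate is pre-specified to read against 0.38 or 0.20, and the SAP's own condition can stop the second K10 comparison from being made.

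**Conclusion.** The concern holds in this form: no evaluation of either benchmark is pre-specified, and the gate in Aim 2b can leave the 0.20 benchmark unestimated on K10. On a two-sample basis, with both arms truly at 0.38, unadjusted two-sided tests and complete data, that happens in about 45% of trials, so roughly half. For the interaction test itself no single figure can be given, because the within-person correlation and the shape of the effect over time are not stated.

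It does not show that the pilot will be misreported or that 0.38 is a go/no-go rule. It is still worth correcting before analysis: the SAP already prefers estimates and intervals where it admits low power (Aim 2c), and the protocol makes the same admission for the Aim 2a comparison at 0.38.

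**What to change.** In SAP Aims 2a and 2b:

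- Pre-specify the K10 difference at a named visit, for example week 8, the end of the intervention. Take it from a model with time as a categorical visit, or another coding that supports a visit-specific contrast.
- Divide it by a pre-defined SD and say which. The baseline SD may be narrowed by the symptom-score entry criteria, which would inflate d.
- Give a 95% CI for each messaging arm versus control, and state how the estimate and interval are read against 0.38.
- Report adaptive versus randomised with a 95% CI against 0.20 regardless of the Aim 2a p-value.
- Keep the interaction test as supportive and the feasibility criteria as the primary aim.

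The cost is SAP wording and a few model contrasts, with no new data. The downside is that the wide intervals, about ±0.4 to ±0.5 SD at 40 per arm, become explicit. They will not separate 0.20 from zero, and readers should be told so.

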We will explore whether engagement targets (engagement) and psychological targets (coping skill use; CB-RSS) mediate treatment effects on psychological distress outcomes (K10) and secondary outcomes (PhQ-9, GAD-7, DSI-SS). Mediation analyses will be conducted only if the necessary preconditions for mediation are met (e.g., a significant effect of intervention condition(s) on the outcome (Aims 2a-2c), and a significant effect of intervention condition(s) on the proposed target (engagement or coping skill use; CB-RSS)).

If these conditions are met for an outcome/target pair, we will use generalized linear models to estimate paths a (intervention to target) and b (target to outcome) using appropriate link functions based on variable distributions. Mediation will be evaluated using the Iacobucci method, which constructs a normally distributed test statistic from standardized regression coefficients. Because these analyses are exploratory and involve multiple parallel models, we will control the false discovery rate (FDR) using the Benjamini-Hochberg procedure, with an FDR threshold of 10% appropriate to pilot mediation work. If the prerequisite conditions are not met for a given mediator or outcome, mediation models for that pair will not be estimated.

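### Aim 2a lets each arm keep its own baseline K10 mean: valid, but it gives up precision that a common baseline with categorical time would recover at no data cost

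*SAP*

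**What the plan says.** SAP Aim 2a makes K10 the primary outcome and fits one mixed model per outcome with "fixed effects for treatment arm, time, and the treatment by time interaction", a participant random intercept and autoregressive errors. The primary inference is the "treatment by time interaction to determine whether either intervention produces a different rate of change over time compared to control". On covariates it says only "Secondary models will control for baseline demographic covariates (e.g., age, sex, race, ethnicity", where the list ends. Neither baseline K10 as a covariate nor a common baseline mean is mentioned. Time is not declared linear or categorical.

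Protocol 4.0 (Clinical Trial) has baseline measures completed before participants are randomised. Protocol 14.0 lists the major assessments as baseline and weeks 4, 8, 12 and 16. The intervention lasts 8 weeks.

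Protocol 3.0 states 80% power at d=0.64 with 40 per group, expects about d=0.38, concedes that this is below what the trial can detect, and says of it that "it serves as a useful benchmark in determining whether the intervention shows sufficient value to pursue a larger trial".

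The Aim 2a result is used later. Aim 2b runs for an outcome only if there is a "significant difference between at least one messaging intervention and the control group for a given outcome", and Aim 3 requires a significant intervention effect before mediation is tested.

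**The concern.** When baseline is measured before randomisation, the arms share one true baseline mean by design. A model with a free arm effect estimates a separate baseline mean for each arm, so the interaction becomes a comparison of changes. That comparison is unbiased, but it carries all of the baseline noise. A common baseline, or baseline K10 as a covariate, removes the part of that noise that does not predict follow-up.

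The stakes are modest but real. The pilot's product is an estimate to set against d=0.38, and a wider interval makes it less useful. The same p-value decides, outcome by outcome, whether Aim 2b is run, and it feeds the Aim 3 precondition.

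A smaller, separate matter is that the SAP does not say which quantity becomes the d compared with 0.38.

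**Working it through.** **Inputs from the documents.** 40 per arm; d=0.64 and d=0.38 (protocol 3.0); visits at weeks 0, 4, 8, 12 and 16 (protocol 14.0); random intercept plus autoregressive errors (SAP Aim 2a).

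**Assumptions not in the documents.** Two-sided 5%; SD 1 at each visit; complete data; random-intercept share of variance (ICC) 0.2, 0.4 or 0.6; residual autocorrelation 0.3 per visit. One messaging arm is compared with control.

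**1. The plan's own figure.** Two-sample t-test, 40 v 40, d=0.64: noncentrality 0.64 × √(40/2) = 2.86, power 80.7%. The stated 80% reproduces as a single-time comparison on complete data. At 32 per arm (80% of 40): 0.64 × √(32/2) = 2.56, power 71%.

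**2. Baseline-to-week-8 correlation.** Week 8 is two visits after baseline, so r = ICC + (1 − ICC) × 0.3². This gives 0.2 + 0.8 × 0.09 = 0.272; 0.4 + 0.6 × 0.09 = 0.454; 0.6 + 0.4 × 0.09 = 0.636.

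**3. Variance of the week-8 difference between arms.**
- Free baselines (change): (2/40) × 2(1 − r)
- Common baseline or baseline covariate: (2/40) × (1 − r²)
- Ratio: 2/(1 + r), which does not depend on the sample size

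Power is Φ(d/SE − 1.96).

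| | ICC 0.2 | ICC 0.4 | ICC 0.6 |
|---|---|---|---|
| SE, free baselines | 0.270 | 0.234 | 0.191 |
| SE, common baseline | 0.215 | 0.199 | 0.173 |
| Variance ratio | 1.572 | 1.376 | 1.222 |
| Equivalent n per arm (ratio × 40) | 63 | 55 | 49 |
| 95% CI half-width, free | 0.53 | 0.46 | 0.37 |
| 95% CI half-width, common | 0.42 | 0.39 | 0.34 |
| Power at d=0.64, free | 66% | 78% | 92% |
| Power at d=0.64, common | 84% | 89% | 96% |
| Power at d=0.38, free | 29% | 37% | 51% |
| Power at d=0.38, common | 42% | 48% | 60% |

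Example, ICC 0.4: 0.64/0.234 − 1.96 = 0.78, giving 78%; 0.64/0.199 − 1.96 = 1.25, giving 89%.

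Over a wider grid (ICC 0.2 to 0.7, autocorrelation 0, 0.3 or 0.5), power at d=0.64 is 61.9 to 98.9% with free baselines and 83.2 to 99.5% with a common one. The gain appears throughout, because 2/(1 + r) exceeds 1 whenever r is below 1.

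**4. If time is linear.** For an effect that truly rises in a straight line to 0.64 at week 16, the smaller standard error alone raises slope power from 65/77/91% to 88/91/96%. With other shapes, a common intercept changes what the slope estimates:
- Plateau (0, 0.32, 0.64, 0.64, 0.64): slope × 16 weeks is 0.64 with free baselines but 0.74/0.71/0.69 with a common intercept, although the true difference never exceeds 0.64.
- Gone by week 16 (0, 0.32, 0.64, 0.32, 0): 0 with free baselines, 0.20/0.14/0.09 with a common intercept.

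Categorical time avoids this, because no straight line is forced through the shared starting point.

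**5. Why the contrast should be named.** Suppose the true effect is 0.38 at week 8 and halves by week 16 (0, 0.19, 0.38, 0.285, 0.19). The week-8 contrast reads 0.38. The free-baseline slope × 16 weeks has visit weights −0.874, −0.252, 0, 0.252 and 0.874 at autocorrelation 0.3, so it reads −0.252 × 0.19 + 0.252 × 0.285 + 0.874 × 0.19 = 0.19.

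**The case against.** The strongest reply is that nothing here is invalid. With baseline as the first visit, arm-by-time already compares change from baseline. Feasibility is the stated primary aim, the protocol concedes low power at d=0.38, and the improvement does not alter that. All of this stands. It limits the point to efficiency and clarity, but it is no reason to leave out a gain that costs nothing.

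Several stronger readings are tempting, and the documents do not support them:
- *Baseline is ignored.* It is not, if it enters as the first repeated measure.
- *No primary contrast is named.* Too strong. Aim 2a names the outcome, the comparator, both arms and the inferential term, and its reference to a rate of change points to a slope. What is missing is explicit time coding and the quantity to be read against 0.38.
- *The slope is the wrong target.* Week 8 versus the 16-week trajectory is a choice of estimand. If benefit keeps growing after treatment, the slope has more power.
- *A common baseline helps equally under any time coding.* It does not. For the plateau above, common-intercept slope power comes out at 95/95/98%, but part of that comes from the overstated estimate.
- *The 80% at d=0.64 is wrong.* It reproduces.

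The K10 row of the assessment table cannot be read with certainty in the text available to me, so the first K10 may belong to screening rather than week 0. Either precedes randomisation, so the argument holds, but a longer gap could lower r.

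**Conclusion.** The point holds as an avoidable loss of precision in the Aim 2a primary model. For a week-8 contrast, a common baseline or baseline covariate is worth the precision of 63, 55 or 49 per arm instead of 40, at assumed correlations of 0.27, 0.45 and 0.64. The size depends on that correlation, on complete data and on the assumed covariance. Missing data would lower both sets of power figures. The direction does not depend on the correlation chosen.

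The trial would still not be decisive at d=0.38. The unstated time coding is mostly missing detail, and the power sentence needs a label rather than a correction.

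**What to change.** In SAP Aim 2a, for the primary model:
1. Enter time as categorical and constrain the arms to a common baseline mean (visit effects plus arm-by-visit effects after baseline, with no separate arm effect at baseline). Alternatively, use baseline K10 as a covariate with weeks 4, 8, 12 and 16 as outcomes. The other outcomes with a pre-randomisation value can be handled in the same way.
2. State which contrast of each messaging arm with control gives the d to be compared with 0.38, for example week 8 or the 16-week slope. The choice is the sponsor's. If a linear slope is kept as primary, say so, and do not add a common intercept without allowing for a non-linear effect.
3. In protocol 3.0, label the 80% at d=0.64 as a complete-data, single-time comparison of 40 v 40, or restate it for the chosen contrast with its assumed correlation and missing data.

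The cost is a few sentences, with no new data, visits or participants. The trade-off lies in the choice of contrast: a week-8 contrast gives up power relative to a slope if the benefit continues to grow after week 8.
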